#### **8.4.1.3. Natural log (ACR)/eGFR**

Mean ratios of natural log (ACR)/eGFR (Section 6.5.8) are summarized at each time point for safety. The ratio of natural log (ACR)/eGFR by analysis visit is summarized by arithmetic means for safety.

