5.1.1. Efficacy

As seen in [Table 3](#), improvements in renal function, including eGFR, creatinine clearance, and inulin clearance, have been observed with bardoxolone methyl treatment in multiple clinical studies, including those in CKD, cancer, and PH patients. Bardoxolone methyl was originally considered for development in cancer patients, and in two Phase 1 studies, bardoxolone methyl was observed to reduce serum creatinine levels, corresponding to an increase in eGFR. The reductions of serum creatinine levels and resultant increases in eGFR were time-dependent and manifested in a majority (82%) of the patients studied. In subsequent studies that enrolled over 2,700 patients with type 2 diabetes and CKD, bardoxolone methyl has been shown to consistently produce clinically and statistically significant improvements in eGFR that are durable for at least one year in treated patients.

Study 402-C-0804 (BEAM) was a multicenter, randomized, double-blind, placebo-controlled, parallel-group, multi-dose, Phase 2b study designed to assess the efficacy and safety of 3 doses (25, 75, and 150 mg) of the crystalline formulation of bardoxolone methyl in patients with Stage 3b-4 CKD (eGFR 20-45 mL/min/1.73 m²) and type 2 diabetes. Analysis of the primary endpoint, the change in eGFR values from baseline at Week 24, demonstrated a clinically and statistically significant increase in eGFR relative both to the baseline value and to the change with placebo ($p < 0.001$) at each of the 3 tested dose levels ([Pergola, 2011](#)). Mean eGFR increases were largely sustained through Week 52 and on average, patients treated with bardoxolone methyl experienced a net increase in eGFR of 7.4 ± 0.8 mL/min/1.73 m² at Week 52 from a baseline of 32.4 mL/min/1.73 m².

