5.1.2.6. Increases in Urinary Protein

Increases in urinary albumin have been observed in some patients treated with bardoxolone methyl with CKD and type 2 diabetes. The increases are likely due to bardoxolone methyl's pharmacological modulation of tubular protein reabsorption and have not been associated with interstitial fibrosis or injury. In preclinical studies, bardoxolone methyl has been shown to downregulate the primary proteins involved in protein reabsorption in the proximal tubules: the megalin-cubilin complex. Moreover, the magnitude of observed eGFR increases with bardoxolone methyl treatment is thought to reduce the residence time of protein in the proximal tubules, thereby reducing protein reuptake and increasing urinary protein levels. Therefore, increased eGFR, together with decreased megalin expression, is thought to result in decreased fractional reabsorption of albumin and increased urinary excretion of albumin. Consistent with bardoxolone methyl-mediated protection in preclinical models of protein-overload-induced nephropathy, these pharmacological effects are thought to reduce protein overload and secondary nephropathy caused by excessive albumin uptake and therefore are not associated with tissue injury and interstitial fibrosis.

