9.1.6. Management of Urinary Protein

Although increases in urinary protein with bardoxolone methyl have not been associated with renal injury or loss of kidney function, investigators should closely monitor patients if urinary albumin to creatinine ratios increase by more than 100% and exceed 1000 mg/g for proteinuria and should consult the medical monitor for appropriate measures.

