#### **6.5.8. Natural log (ACR)/eGFR**

To evaluate ACR after adjusting for filtration rate,  $\ln(ACR)/eGFR$  (Section 6.5.7 and Section 6.5.6) is calculated.

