#### **8.4.1.1. Urine Albumin/Creatinine Ratio**

Summaries of ACR (Section 6.5.7) will use the geometric mean with 95% confidence intervals instead of the arithmetic mean and will display ACR results in original units of mg/g. Changes from baseline in ACR are reported as the post-baseline/baseline ratios and are summarized by geometric means with 95% confidence intervals at each time point. Summaries of ACR will use the geometric mean instead of the arithmetic mean. Presentations will display ACR results in the original units (mg/g). Changes in ACR are calculated as the ratio of each visit to baseline.

Additionally, ACR is summarized by baseline ACR quartile. Descriptive summaries at each visit include the geometric mean of ACR, SD as well as the geometric mean of percent change from baseline. Summaries of ACR exclude values within the Week 2 and Week 6 visit windows.

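### ln(ACR)/eGFR can move against a large ACR change when eGFR also changes, and its direction depends on the ACR unit, so it is not a valid filtration adjustment

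*SAP*

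**What the plan says.** SAP 6.5.8 gives the purpose of the index: "To evaluate ACR after adjusting for filtration rate". The formula is the natural log of ACR divided by eGFR, with eGFR left on its raw scale. SAP 8.4.1.3 sets the summary: "The ratio of natural log (ACR)/eGFR by analysis visit is summarized by arithmetic means for safety". No unit is named for the index, and nothing is said about how to read its direction.

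ACR itself is handled differently. SAP 6.5.7 works in mg/g, and SAP 8.4.1.1 uses geometric means and a relative change: "Changes in ACR are calculated as the ratio of each visit to baseline". That change is the same in any unit.

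The protocol describes eGFR and urinary albumin rising together on drug. Section 5.1.2.6 reports: "Increases in urinary albumin have been observed in some patients treated with bardoxolone methyl with CKD and type 2 diabetes". It attributes the rise partly to the increase in eGFR.

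**The concern.** A logged numerator over an unlogged denominator does not remove the effect of filtration from ACR. ln(ACR) changes slowly when ACR changes by a large factor, whereas dividing by eGFR passes on the full proportional change in eGFR. A modest eGFR rise can therefore outweigh a doubling of ACR.

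Change from baseline in ACR is part of the primary endpoints (SAP 3.2.1), and this index is the only planned summary that I find of ACR net of filtration. If its visit mean falls, a reader could conclude that albuminuria has not risen once filtration is allowed for, when ACR has in fact doubled.

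**Working it through.** Write I = ln(A)/G, with A for ACR, G for eGFR, and subscripts 0 and 1 for baseline and follow-up. The SAP gives no figure for the index to reproduce.

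**Inputs**
- eGFR pair from BEAM, protocol 5.1.1: "patients treated with bardoxolone methyl experienced a net increase in eGFR of 7.4" and "at Week 52 from a baseline of 32.4" mL/min/1.73 m². So 32.4 becomes 39.8, and 7.4/32.4 = +22.8%. BEAM enrolled type 2 diabetes with CKD, so it serves only to show the mechanism.
- eGFR rise of 9.5, protocol Table 3, 402-C-1603 Year 1. This is a placebo-corrected difference, used here as an assumed change within a patient.
- Baseline eGFR of 40, 60 and 80: assumptions, as the documents give none for EAGLE.
- ACR doubling: an assumption, as the documents give no size for the rise. For scale, protocol 9.1.6 asks for close monitoring "if urinary albumin to creatinine ratios increase by more than 100% and exceed 1000 mg/g for proteinuria"; that is a trigger, not an observed effect.
- Baseline ACR of 30, 300 and 1000 mg/g: category limits in SAP 6.5.7.1.

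**1. Direction.** For A0 above 1 mg/g, I falls when G1/G0 > ln(A1)/ln(A0). After a doubling, the eGFR rise that just cancels it is ln 2/ln(A0):
- A0 = 30: 0.693/3.401 = 20.4%
- A0 = 300: 0.693/5.704 = 12.2%
- A0 = 1000: 0.693/6.908 = 10.0%

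With the BEAM pair and ACR 300 to 600: ln 300/32.4 = 0.1760 and ln 600/39.8 = 0.1607, a fall of 8.7%. At constant eGFR the index follows ACR: a doubling from 300 gives +12.2%.

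**2. Unit.** Multiplying ACR by a constant c shifts the change in I by ln(c) × (1/G1 − 1/G0), which is zero only if eGFR does not change. The same patient in g/g: ln 0.3/32.4 = -0.0372 and ln 0.6/39.8 = -0.0128, a rise. Check: ln(0.001) × (1/39.8 − 1/32.4) = +0.0396; added to the mg/g change of -0.0153, this gives +0.0243, which matches the g/g change.

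**3. Assumed EAGLE range.** The relative change in I after a doubling is [ln(2·A0)/ln(A0)]/(1 + 9.5/G0) − 1:

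| Baseline ACR (mg/g) | eGFR 40 | eGFR 60 | eGFR 80 |
|---|---|---|---|
| 30 | -2.7% | +3.9% | +7.6% |
| 300 | -9.4% | -3.2% | +0.2% |
| 1000 | -11.1% | -5.0% | -1.6% |

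The index reverses when baseline eGFR is below 9.5 × ln(A0)/ln 2, that is 46.6, 78.2 and 94.7 for the three rows.

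**4. Smaller eGFR rise.** In the protocol, change from baseline is smaller than the placebo-corrected difference: 5.5 against 6.4 in BEACON and 7.4 against 8.6 in BEAM, both about 0.86. Applying 0.86 to 9.5 (an assumption) gives about 8.2. The row for ACR 300 then becomes -6.9%, -1.3% and +1.7%.

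**5. Opposite case, assumed.** The documents describe no fall in ACR alongside a fall in eGFR. Taking the 30% eGFR decline that SAP 8.4.2.2 uses as a threshold, and assuming that ACR halves from 300 to 150: (ln 150/ln 300)/0.7 = 1.255, so the index rises by 25.5%.

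**6. Same scale for both terms.** ln(A/G) changes by ln(A1/A0) − ln(G1/G0), which is free of units. For the doubling with the BEAM pair: 0.693 − 0.206 = +0.487, a ratio of 1.628.

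**The case against.** The strongest reply has three parts.

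- **A measure adjusted for filtration is allowed to differ from ACR.** This stands: no section establishes ACR/eGFR as the true adjustment, and ln(ACR/eGFR) can also diverge from ACR. The case therefore does not rest on divergence alone. It rests on how small an eGFR change is enough, and on a direction that changes with the unit, which needs no view on the right adjustment.
- **No table will be printed in g/g.** This also stands. A reader might infer that the reported value is ambiguous, but SAP 6.5.7 and 8.4.1.1 work in mg/g throughout. The unit result is a diagnosis of the index, not a reporting risk.
- **The misreading is guarded against.** Largely true. ACR ratios to baseline with 95% confidence intervals, ACR shift tables, the count above 3500 mg/g and eGFR changes by visit are all reported separately. The analyses are descriptive, and no decision rule uses the index. A doubling of ACR would be visible elsewhere in the report.

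What remains is that this one table does not deliver the purpose that SAP 6.5.8 states for it.

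**Conclusion.** The point holds in a limited form. Because only ACR is logged, ln(ACR)/eGFR can move against a large ACR change when eGFR also changes, and the direction of its change depends on the ACR unit. It is not a valid filtration adjustment.

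A reader might infer that the index will generally reverse in EAGLE. The documents do not support that. They give neither a baseline eGFR for EAGLE nor a size for the ACR rise, and the BEAM example comes from another population. Under the stated assumptions a doubling of ACR changes the index by anything from -11.1% to +7.6%. Reversal is most likely at high ACR and low eGFR, is absent at low ACR with higher eGFR, and weakens if the eGFR rise within patients is smaller than 9.5.

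A reader might also infer that the ACR safety assessment as a whole is compromised. It is not: the harm is confined to misreading one descriptive table. The change is worth making because the stated purpose is not met and the remedy is cheap.

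**What to change.** In SAP 6.5.8 and 8.4.1.3, define the filtration-adjusted measure as ln(ACR/eGFR) = ln(ACR) − ln(eGFR), using ACR as imputed under SAP 6.5.7. Report it by visit as the geometric mean ratio to baseline with a 95% confidence interval. This matches the treatment of ACR in SAP 8.4.1.1, and the ratio does not depend on the unit. ln(ACR)/eGFR may be kept as a supplement.

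The cost is SAP wording and one extra derived variable from data already collected. The new measure reduces divergence from ACR but does not remove it: it still falls when eGFR rises proportionally more than ACR. For example, ACR +10% with eGFR 60 to 69.5 gives 1.10/1.158 = 0.950, or -5.0%. After a doubling of ACR it falls only if eGFR itself more than doubles.

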### **8.4.2. Categorical Summaries of Laboratory Results**

The number and percentage of patients by laboratory normality and abnormality categories at any time during the study (Normal, Low, High) are summarized by treatment analysis group (Section 4.5), laboratory category (hematology, chemistry, and urinalysis), and laboratory test. The worst abnormality values are defined as the maximum values while on study treatment (ie, up to < 14 days after last dose), except for magnesium and hemoglobin. The worst abnormal values for magnesium and hemoglobin are defined as the minimum values while on study treatment.

An initial set of parameters of specific interest (ALT, AST, ACR) are summarized using shift tables, though additional parameters may be added as appropriate. Shift tables summarizing (1) baseline to end of treatment, and (2) baseline to worst on-treatment, (3) baseline to follow-up, and (4) worst on-treatment to follow-up are presented for lab parameters as appropriate. For ACR, summaries will present shifts from/to the categories in Section 6.5.7.1. For ALT and AST, summaries will present shifts from/to the following categories:

- $< 3 \times$  upper limit of normal (ULN)
- $\geq 3 \times$  ULN to  $< 5 \times$  ULN
- $\geq 5 \times$  ULN to  $< 10 \times$  ULN
- $\geq 10 \times$  ULN to  $< 20 \times$  ULN
- $\geq 20 \times$  ULN

In addition, a summary table is provided by treatment analysis group (Section 4.5) for the number and percentage of patients meeting a following pre-specified threshold level at any time during the study:

- ACR  $> 3500$  mg/g
- Magnesium  $< 1.3$  mEq/L (0.65 mmol/L)
- BNP  $> 200$  pg/mL
- N-terminal prohormone BNP  $> 1000$  pg/mL

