b After the Week 24 visit, subjects will continue to be assessed in person every 24 weeks until the study ends. The End-of-Study visit should occur within 30 days after bardozone methyl becomes available to the subject through commercial channels. Subjects who will be discontinued from the study prior to commercial availability of bardozone methyl must also complete all End-of-Study assessments as soon as possible (if possible, within 30 days of discontinuation).

c On Day 1, all procedures should be performed before study drug administration. AE assessment on Day 1 should be performed following study drug administration. If the Day 1 visit for EAGLE is the same as the end-of-study visit for CARDINAL (all versions) or FALCON (protocol version 5 and older), the laboratory assessments required for both visits should only be completed once.

If the Day 1 visit for EAGLE is the same as the end-of-study visit for FALCON (protocol version 6 and newer), the lab assessments required for both visits should be completed for each study individually.

d Demographics are to be performed on the earliest study visit, whether it be Day 1 or a Screening visit, if necessary.

e Assessment should include a complete physical examination as described in the protocol.

f A serum pregnancy test will be performed at any point in time if a pregnancy is suspected. All other pregnancy assessments will be urine pregnancy tests. Additional pregnancy assessments will be performed more frequently if required by local law or requested by local health authorities or IRBs/IECs.

g eGFR will not be calculated by the central lab.

h Urine ACR will be measured by first morning void spot urine collection. Appropriate containers for the collection will be provided to the subject at the visit prior to collection.

i Adolescent patients from the FALCON (402-C-1808) ( $12 \leq \text{age} < 18$  years at consent) will be assessed by Tanner staging at all specified timepoints.

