#### 6.5.4. Visit Windows

**Table 2: Visit Window (Days)**

Analysis Visit	Label	Target Study Day	Analysis Window
0	Day 1	1	1
1	Week 1	7	$2 \leq \text{Study Day} \leq 10$
2	Week 2	14	$11 \leq \text{Study Day} \leq 21$
4	Week 4	28	$22 \leq \text{Study Day} \leq 35$
6	Week 6	42	$36 \leq \text{Study Day} \leq 49$
8	Week 8	56	$50 \leq \text{Study Day} \leq 70$
12	Week 12	84	$71 \leq \text{Study Day} \leq 126$
24	Week 24	168	$127 \leq \text{Study Day} \leq 210$
48	Week 48	336	$308 \leq \text{Study Day} \leq 364$
72	Week 72	504	$476 \leq \text{Study Day} \leq 532$
96	Week 96	672	$644 \leq \text{Study Day} \leq 700$
120, 144, etc.	Week 120, Week 144, Every 24 Weeks Thereafter	Analysis Visit $\times$ 7	$([\text{Analysis Visit} \times 7] - 28) \leq \text{Study Day} \leq ([\text{Analysis Visit} \times 7] + 28)$
FU	Follow-up	28 days after last dose	$14 \leq \text{Days after last dose}^a \leq 35$

a For safety analyses, last dose for patients completing the treatment or permanently discontinuing study drug that occur on the date of last dose or less than 14 days after last dose are considered on treatment.

The safety follow-up is based on days since last dose. If more than one assessment exists during the follow-up after last dose, the one closest to 28 days following the date of the last study drug administration is used for analysis and summary.

If a parameter is assessed or measured more than once within a visit window, the one that is closest to the protocol-scheduled time point (or target study day) is used for the purposes of data analysis and summary. If two assessments are equidistant from a target study day, the earlier assessment is used. If the visit used for analysis includes two assessments on the same day, the average of assessments will be used for non-laboratory parameters. For laboratory parameters, if both an original and retest result are available in the laboratory dataset, the original result will be used and the second (ie, “retested”) result will be ignored. Records from visits not closest to the target study day, and therefore not used in analyses, are presented in by-subject data listings.

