**Table 3: Pre-specified Threshold Levels for Transaminases**

Lab Parameter	Threshold
ALT, AST	$\geq 3 \times$ ULN and $< 5 \times$ ULN
	$\geq 5 \times$ ULN and $< 10 \times$ ULN
	$\geq 10 \times$ ULN and $< 20 \times$ ULN
	$\geq 20 \times$ ULN
	$\geq 5 \times$ ULN for more than 2 weeks
TBL	$\geq$ ULN and $\leq 1.5 \times$ ULN
	$> 1.5 \times$ ULN and $\leq 2 \times$ ULN
	$> 2 \times$ ULN
ALT, AST, TBL	ALT or AST $> 3 \times$ ULN and TBL $> 1.5 \times$ ULN
	ALT or AST $> 3 \times$ ULN and TBL $> 2 \times$ ULN
ALP	$> 1.5 \times$ ULN

Abbreviations: ALP=alkaline phosphatase; ALT=alanine aminotransferase; AST=aspartate aminotransferase; TBL=total bilirubin; ULN=upper limit of normal.

A summary table that includes frequencies and percentages of patients that meet any of the above criteria at any time during the study is provided. A listing of subjects with abnormal ALT, AST, or TBL will also be provided.

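### SAP 8.4.2 takes the highest on-treatment value as the worst for every laboratory test except magnesium and hemoglobin, and does not say whether the Normal/Low/High table uses that rule or counts any occurrence

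*SAP*

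**What the plan says.** SAP 8.4.2 opens with a table that counts patients by "laboratory normality and abnormality categories at any time during the study (Normal, Low, High"), split by treatment analysis group, laboratory category and test.

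The worst-value rule comes next: "The worst abnormality values are defined as the maximum values while on study treatment". On treatment ends just short of 14 days after the last dose. There are two exceptions: "The worst abnormal values for magnesium and hemoglobin are defined as the minimum values while on study treatment".

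The following paragraph introduces the shift tables. ALT, AST and ACR are named, "though additional parameters may be added as appropriate". Two of the four shifts use the worst on-treatment value: from baseline to worst, and from worst to follow-up.

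Elsewhere the same whole-study phrase plainly means that a criterion was ever met. SAP 8.4.2.1, for example, counts patients who "meet any of the above criteria at any time during the study".

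**The concern.** For hematocrit, RBC count and albumin, the highest value a patient recorded is the most reassuring one, not the worst. For potassium, sodium, calcium, phosphorus, neutrophils and platelets, either direction can matter, and a maximum shows only one. The SAP accepts this for hemoglobin but leaves hematocrit and RBC count, from the same blood count, at the maximum. Phosphorus is not an idle example: the protocol introduction reports phosphate reductions with this drug.

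The rule sits between the Normal/Low/High table and the shift tables, and no sentence says which it serves. Two programmers could produce different Low counts from the same data. Safety is the primary endpoint of this study, and the Normal/Low/High table is where a reader would look for the number of patients with a low result on each test.

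**Working it through.** The plan gives no figure to reproduce, so the check is to follow each reading of the text.

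**Does the rule reach the Normal/Low/High table?**

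- For: the rule comes straight after that table's sentence, before shift tables are mentioned, and repeats its term for abnormality. Its exceptions, magnesium and hemoglobin, are not among the named shift-table tests. If the rule served only ALT, AST and ACR, the exceptions would have no use.
- Against: the table has its own criterion, and the same phrase means ever met in the threshold table of 8.4.2 and in 8.4.2.1. The term worst on-treatment is attached by name only to shift tables.

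Both readings are fair, and the text does not choose between them.

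**What each reading does to one patient.** SAP Table 1 schedules chemistry and hematology at Weeks 1, 2, 4, 6, 8, 12 and 24, which is 7 on-treatment visits to Week 24. Let x1 to x7 be the values and LLN the lower limit of normal.

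- Maximum rule: Low if max(x1,…,x7) < LLN, so all 7 values must be low.
- Any occurrence: Low if min(x1,…,x7) < LLN, so one low value is enough.

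| Pattern over 7 visits | Maximum rule | Any occurrence |
|---|---|---|
| 7 low | Low | Low |
| 6 low, 1 normal | Normal | Low |
| 1 low, 6 normal | Normal | Low |
| 1 low, 1 high, 5 normal | High | Low and High |

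The two readings agree only in the first row. In the last row, even the any-occurrence reading is incomplete, because the SAP does not say how a patient with both Low and High values is counted. Magnesium and hemoglobin escape the problem of missed low values, since under the minimum one low value is enough.

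**Period.** The table covers the whole study. The rule covers treatment only, and the footnote to SAP Table 2 agrees with its cut-off: assessments "less than 14 days after last dose are considered on treatment". Two sets of results fall inside the first period and outside the second:

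- Screening and Day 1 results. SAP Table 1 says: "On Day 1, all procedures should be performed before study drug administration".
- Results 14 or more days after the last dose. Patients who discontinue before commercial availability "must also complete all End-of-Study assessments as soon as possible (if possible, within 30 days of discontinuation"), so End-of-Study laboratory results can fall on either side of the cut-off.

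**Shift tables.** For ALT, AST and ACR, high is the concern and the maximum is correct. Any low-concern or two-sided test added later would take the maximum by default.

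**The case against.** The strongest reply is that no named output is wrong. The only outputs expressly built on the worst value are shift tables for three tests, and those run the right way. The Normal/Low/High table has its own criterion, most naturally read as ever met. The magnesium and hemoglobin exceptions may simply anticipate tests added to the shift tables later.

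Other routes also remain. Magnesium below 1.3 mEq/L has its own count, and eGFR loss is analysed in SAP 8.4.2.2. Selected tests are summarised by visit with minima, out-of-range results are flagged in listings, and clinically significant changes are reported as adverse events. Hemoglobin, at the minimum, already picks up much of what hematocrit and RBC count would show.

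Most of this stands and limits the point, but it does not remove it. If the exceptions are there for added tests, the rule is meant to govern added tests, and its default is then wrong for those where low is the concern. None of the other routes gives a per-test count of patients with a Low value.

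A reader might infer three stronger things that the documents do not support:

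- That Low counts will be lost. That follows under one reading only.
- That the Normal/Low/High table has no stated period. It has one; what is missing is a statement of how it relates to the on-treatment period of the adjacent rule.
- That nearly the whole panel is analysed in the wrong direction because only two tests take the minimum. For ALT, AST, bilirubin, GGT, LDH, CK, creatinine, BUN and others, the maximum is the right choice. Counting tests assigned the maximum therefore does not measure the error.

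**Conclusion.** The default-maximum rule is wrong as written for low-concern tests and incomplete for two-sided tests. Whether it also distorts the Normal/Low/High table depends on a link that the SAP leaves unstated. If it does, a patient is Low for a test other than magnesium or hemoglobin only when every on-treatment value is low. If it does not, the handling of patients with both Low and High values is still missing.

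The effect is confined to per-test Low counts and to any low-concern or two-sided test added to the shift tables. The named shift tables stand, and all analyses are descriptive. The documents give no rate of low values, so the number of patients who would change class cannot be estimated. The point is minor, with moderate confidence. It assumes only that low values are of interest for the tests named above, as the SAP already accepts for hemoglobin and magnesium.

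**What to change.** Make two changes in SAP 8.4.2.

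1. For each quantitative test in the Normal/Low/High table, show patients with any Low value and patients with any High value as separate rows. Allow a patient to appear in both, and define Normal as neither. State one period. From after the first dose to less than 14 days after the last dose is one option, since the section already uses that cut-off.
2. Replace the default maximum with a worst direction set by test: the minimum where low is the concern, the maximum where high is the concern, and both for two-sided tests. Apply this to any test added to the shift tables.

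The cost is a few sentences or a short table in the SAP and minor programming. No new data are needed.
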